## **11.1 Management of Study Patients During Local Epidemic or Pandemic**

In the event of ongoing or worsening COVID-19 outbreaks locally or regionally (or other widespread viral illnesses that strain health systems and require modification of normal operations), efforts to reduce visits and exposure for patients will be permissible, where permitted by law, institutional policy, and NCI requirements. All efforts should be made to follow the study protocol and study calendar without deviation. When this is not feasible or safe, the following modifications can be considered. These modifications should be used to make it feasible for patients remain on study instead of withdrawing.

- All labs and visits are required to be maintained per the study calendar.
- Excluding screening and cycle 1 day 1, outside facilities may be used for laboratory assessments
- Excluding screening and cycle 1 day 1, remote visits (telehealth) may be used in place of in person visits. Video telemedicine visits are strongly preferred over telephone only encounters to accurately assess adverse events.
- Days 2-3 of etoposide may be administered as oral dose of 200 mg/m^2 PO daily. (Cycles 1-4, day 1 carboplatin and etoposide will need to be administered at study facility as per study protocol)
- For patients in the maintenance phase, atezolizumab may be given every 4 weeks per FDA labeled dosing schedule of 1680 mg every 4 weeks.
- Local infusion facilities not part of the study facilities may be used for maintenance atezolizumab.
- Entinostat can be shipped directly to the patient up to two bottles at a time.

## 12. MEASUREMENT OF EFFECT

Although the clinical benefit of these drugs has not yet been established, the intent of offering this treatment is to provide a possible therapeutic benefit, and thus the patient will be carefully monitored for tumor response and symptom relief in addition to safety and tolerability. Patients with measurable disease will be assessed by standard criteria. For the purposes of this study, patients should be re-evaluated every 6 weeks during year 1, every 3 months during year 2, and every 6 months thereafter. In addition to a baseline scan, confirmatory scans will also be obtained 6 weeks following initial documentation of an objective response.

### 12.1 Antitumor Effect – Solid Tumors

Response and progression will be evaluated in this study using the new international criteria proposed by the revised Response Evaluation Criteria in Solid Tumors (RECIST) guideline (version 1.1) [Eur J Ca 45:228-247, 2009]. Changes in the largest diameter (unidimensional measurement) of the tumor lesions and the shortest diameter in the case of malignant lymph nodes are used in the RECIST criteria.

#### 12.1.1 Definitions

Evaluable for Toxicity. All patients will be evaluable for toxicity from the time of their first treatment with entinostat.

Evaluable for Objective Response. Only those patients who have measurable disease present at baseline, have received at least one cycle of therapy, and have had their disease re-evaluated will be considered evaluable for response. These patients will have their response classified according to the definitions stated below. (Note: Patients who exhibit objective disease progression prior to the end of cycle 1 will also be considered evaluable.)

Evaluable Non-Target Disease Response. Patients who have lesions present at baseline that are evaluable but do not meet the definitions of measurable disease, have received at least one cycle of therapy, and have had their disease re-evaluated will be considered evaluable for non-target disease. The response assessment is based on the presence, absence, or unequivocal progression of the lesions.

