## 6. TREATMENT PLAN

### 6.1 Agent Administration

Treatment will be administered on an outpatient basis (inpatient is allowed if clinically indicated). Reported adverse events and potential risks are described in Section 10. Appropriate dose modifications are described in Section 7. No investigational or commercial agents or therapies other than those described below may be administered with the intent to treat the patient's malignancy.

Patients will receive up to 4 cycles of induction treatment followed by maintenance treatment for a total of 1 year of combined treatment (or 17 cycles). Patients who are unable to tolerate carboplatin and etoposide may discontinue induction and receive maintenance treatment for the remaining duration of treatment. Order of administration during induction should be according to institutional standard. Entinostat should be taken prior to administration of other agents.

On day 1, when patient receives additional therapy, entinostat will be administered prior to other chemotherapy or immunotherapy agents. On day 1 of induction cycles, Atezolizumab will be administered first, followed by carboplatin, and lastly etoposide. Time intervals between infusions are per institutional standards.

Dose Escalation Schedule								
Dose Level	Induction (Cycles 1-4)				Maintenance (Cycles 5-17)		Cycle Length	
	Dose				Dose			
	Carboplatin	Etoposide	Atezolizumab	Entinostat	Atezolizumab	Entinostat		
Level -1 (ME)	AUC 5 IV D1	100 mg/m  IV D1-3	1200 mg IV D1	None	1200 mg IV D1	5 mg PO D1, 8, 15	21 days	
Level 1*	AUC 5 IV D1	100 mg/m  IV D1-3	1200 mg IV D1	2 mg PO D1, 8, 15	1200 mg IV D1	5 mg PO D1, 8, 15	21 days	
Level 2	AUC 5 IV D1	100 mg/m  IV D1-3	1200 mg IV D1	3 mg PO D1, 8, 15	1200 mg IV D1	5 mg PO D1, 8, 15	21 days	
Level 3	AUC 5 IV D1	100 mg/m  IV D1-3	1200 mg IV D1	5 mg PO D1, 8, 15	1200 mg IV D1	5 mg PO D1, 8, 15	21 days	

\*Starting Dose Level.

IV = intravenous, AUC = Area Under Curve, PO = Orally, ME = Maintenance entinostat.

Regimen Description – Induction (up to 4 cycles) #					
Agent	Premedication; Precautions*	Dose	Route	Schedule	Cycle Length
Entinostat	Take on an empty stomach (at least 1 hour before and 2 hours after a meal)	Assigned dose level	PO	Day 1, 8, 15	21 days (3 weeks)
Atezolizumab		1200 mg	IV infusion over 60 ( $\pm 15$ ) minutes**	Day 1	
Carboplatin	Dexamethasone NK1 antagonist 5-HT3 antagonist.	AUC 5***	IV infusion over 30-60 minutes	Day 1	

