# Patients who are unable to tolerate carboplatin and etoposide, may discontinue induction and receive the maintenance regimen. If this occurs, maintenance may begin prior to Cycle 5 and can continue for a total of 1 year of treatment.

\* Entinostat is taken 1 hour before and 2 hours after a meal.

*\*\*If there is no infusion-related reaction after the initial dose, all subsequent doses of atezolizumab can be infused over 30 ( $\pm 10$ ) minutes.*

*PO = Orally, IV = Intravenous, AUC = Area Under Curve*

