## 6.2 Definition of Dose-Limiting Toxicity

Management and dose modifications associated with the above adverse events are outlined in Section 7.

Dose limiting toxicity (DLT) is defined as the occurrence of any of the following toxicities listed below. The DLT period will be from Cycle 1, Day 1 through the first cycle. To be evaluable for a DLT, at least 66% of the prescribed dose of each drug must be received during cycle 1 (i.e., 2 of 3 doses of entinostat must be received or 66% of prescribed carboplatin, etoposide, or atezolizumab dose must be infused to be considered evaluable if no DLT occurred). If treatment-related adverse events result in <66% of drug doses received, patients will be evaluable for DLTs. Any toxicities attributable to cancer or cancer progression will not be considered DLTs.

DLTs if felt to be possibly, probably, or definitely related to entinostat:

- Less than 66% of entinostat (0 or 1 doses) received during the first cycle due to treatment-related adverse event(s)
- Death in the absence of progressive cancer (Any grade 5 adverse event)
- Any adverse event resulting in discontinuation of carboplatin/etoposide chemotherapy prior to Cycle 2
- Any treatment-related toxicity causing delay of more than 3 weeks from planned cycle 2 day 1
- Any  $\geq$  Grade 3 non-hematologic adverse event (non-laboratory), excluding alopecia, uncontrolled nausea or vomiting. Grade  $\geq 4$  uncontrolled nausea or vomiting should be considered a DLT if it persists  $\geq 72$  hours despite maximal medical management.
- Any  $\geq$  Grade 3 non-hematologic laboratory value if medical intervention is required (not including endocrinopathies requiring hormone replacement) or leads to hospitalization

DLTs regardless of relatedness to entinostat (attribution to any study drug):

- Hematologic events
  - Grade  $\geq 4$  febrile neutropenia
  - Grade 4 neutropenia lasting  $>7$  days
  - Grade 3 thrombocytopenia associated with bleeding requiring transfusion or Grade  $\geq 4$  thrombocytopenia.

Dose escalation will proceed within each cohort of 3 patients according to the following scheme. Dose-limiting toxicity (DLT) is defined above.

Escalation/De-escalation Rule												
Number of patients treated	1	2	3	4	5	6	7	8	9	10	11	12
Escalate if # of DLT $\leq$	0	0	0	0	0	0	1	1	1	1	1	1
Deescalate if # of DLT $\geq$	1	1	1	1	2	2	2	2	3	3	3	3
Eliminate if # of DLT $\geq$	NA	NA	2	3	3	3	4	4	4	5	5	5

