## 9. STATISTICAL CONSIDERATIONS

### 9.1 Study Design/Endpoints

This is a phase 1 trial to evaluate the safety and efficacy of various doses of entinostat combined with atezolizumab, carboplatin, and etoposide therapy for patients with treatment naïve ES-SCLC. Four dose levels of entinostat are detailed in Figure 1. The Bayesian optimal interval (BOIN) design will be used to find the maximum tolerated dose (MTD) based on safety (Liu and Yuan, 2015; Yuan et al., 2016). The target toxicity rate for the MTD is 20%. Due to overlapping hematologic toxicities between chemotherapy and entinostat, it may be difficult to separate attributions specifically to entinostat, particularly for thrombocytopenia events. Our DLT definitions will count these more extreme hematologic events at DLTs, although it is recognized that these occur in the setting of carboplatin and etoposide chemotherapy alone. Therefore, it is anticipated that a 20% DLT rate is a conservative estimate of the true DLTs directly related to entinostat. Furthermore, small cell lung cancer is an aggressive malignancy with poor overall survival. Additional toxicity is justified if there is potential for efficacy gains. Dose-limiting toxicities (DLT) will be determined by adverse events occurring during the first cycle of treatment. DLTs are defined in Section 6.2.

The primary endpoints of the study are:

- MTD of entinostat
- Grade 3/4 adverse event rate as defined by CTCAE v5.0
- Number of cycles received of the combination of entinostat, atezolizumab, carboplatin, and etoposide (maximum = 4)

The secondary endpoint of the study is:

- 9-month PFS rate, defined as the proportion of patients alive and without disease progression after 9 months from study enrollment

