### 9.3 Analysis of Secondary Endpoints

Adverse events and DLTs will be summarized by frequency and magnitude. The rate of feasibility of administering entinostat concomitantly with atezolizumab, carboplatin, and etoposide as determined by the proportion of participants who receive 3 or more cycles of the combination, will be calculated with a 90% confidence interval. The Kaplan Meier estimator will be used to estimate survival curves for all time to event endpoints including progression free survival (PFS) and overall survival (OS). The 9 month PFS rate will be estimated with a 90% confidence interval. Anti-tumor endpoints, including measures of tumor response and symptom relief, will be summarized using descriptive statistics. Tumor response will be measured using RESIST 1.1 criteria and reported as overall response rate (ORR) with a 95% confidence interval. Entinostat exposure will be determined for each patient using mixed effects pharmacokinetic modeling. Atezolizumab clearance, including a time-varying rate of change, will be determined for each patient using mixed effects pharmacokinetic modeling. Exposure-response assessments will be assess associations between entinostat exposure with the clinically significant toxicity, PFS and OS. Clearance-response will be assessed between baseline or time-varying atezolizumab clearance with the presence of cachexia, PFS and OS. Biomarker evaluations from exploratory objectives will be summarized using descriptive statistics.

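### Section 12.1.1 starts toxicity evaluability at the first entinostat dose; read literally, this leaves Level -1 induction out of the primary Grade 3/4 adverse event rate

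*Combined protocol and SAP*

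**What the plan says.** All references are to the combined protocol and SAP.

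- **Evaluability.** Section 12.1.1 reads: "All patients will be evaluable for toxicity from the time of their first treatment with entinostat". No other sentence says who is evaluable for toxicity in general, and from when. Section 6.2 has its own rule, based on the share of each drug received, for DLT evaluability.
- **Level -1.** The dose escalation schedule in Section 6.1 lists no entinostat at Level -1 in Cycles 1-4, then 5 mg on Days 1, 8 and 15 of each maintenance cycle. The footnote explains the label: "ME = Maintenance entinostat".
- **Early switch.** Patients who cannot tolerate carboplatin and etoposide may leave induction: "If this occurs, maintenance may begin prior to Cycle 5 and can continue for a total of 1 year of treatment".
- **Order of drugs.** On Day 1, "entinostat will be administered prior to other chemotherapy or immunotherapy agents".
- **Endpoint.** Section 9.1 lists among the primary endpoints: "Grade 3/4 adverse event rate as defined by CTCAE v5.0". It gives no population and no start date.
- **Analysis.** Section 9.3 says only: "Adverse events and DLTs will be summarized by frequency and magnitude".

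**The concern.** The 12.1.1 wording suits Levels 1-3, where the first entinostat dose is also the first dose of anything. It does not suit Level -1. There, three kinds of information fall outside the evaluable period:

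- every adverse event during induction;
- every patient who progresses, dies or withdraws before maintenance entinostat;
- for a patient who switches early because of toxicity, the toxicity that caused the switch.

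The Grade 3/4 rate serves primary objective 1.1.2, safety and tolerability. If Level -1 is reported as a maintenance-only rate among patients who got that far, and Levels 1-3 include up to four cycles of carboplatin and etoposide, a difference between levels reflects the counting window as well as entinostat. A rate pooled over levels, if anyone reports one, would mix the two windows.

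**Working it through.** **1. Where the evaluable period starts**

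| | Levels 1-3 | Level -1 |
|---|---|---|
| First entinostat (6.1) | Cycle 1 Day 1, before the other drugs | Start of maintenance: Cycle 5, or earlier after intolerance of carboplatin/etoposide |
| Induction within the 12.1.1 period | Yes | No |
| Patient who stops before maintenance | Evaluable | Never evaluable |
| Adverse events collected (10.3.1, Section 11) | From Cycle 1 Day 1 | From Cycle 1 Day 1 |

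For a Level -1 patient who completes the plan, 4 of 17 cycles fall outside the period, and these are all the carboplatin/etoposide cycles.

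**2. Reproducing the plan's own figures**

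The BOIN design was re-simulated with 10,000 trials per scenario: target 0.20, cohorts of 3 starting at Level 1, maximum 36, stop at 12 on a dose when the decision is to stay, MTD by isotonic regression. The interval parameters are not stated in the plan. Taking 0.6 and 1.4 times the target gives boundaries of 0.157 and 0.238, which reproduce the printed escalation and de-escalation rows exactly. The 0.95 posterior rule reproduces the elimination row.

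| | Sc. 1 | Sc. 2 | Sc. 3 | Sc. 4 |
|---|---|---|---|---|
| Level -1 selected, 9.1.3 (%) | 2.89 | 7.41 | 29.55 | 51.73 |
| Level -1 selected, re-simulated (%) | 2.75 | 7.45 | 29.91 | 51.57 |
| Treated at Level -1, 9.1.3 (%) | 5.6 | 10.6 | 25.7 | 41.3 |
| Treated at Level -1, re-simulated (%) | 5.4 | 10.8 | 26.0 | 41.0 |
| Average N, 9.1.3 | 23.7 | 23.7 | 22.3 | 19.4 |
| Average N, re-simulated | 23.6 | 23.7 | 22.1 | 19.6 |

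The stated figures hold.

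**3. How many patients are affected**

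Expected number at Level -1 = share treated there × average N, from 9.1.3:

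- Scenario 1: 0.056 × 23.7 = 1.3
- Scenario 2: 0.106 × 23.7 = 2.5
- Scenario 3: 0.257 × 22.3 = 5.7
- Scenario 4: 0.413 × 19.4 = 8.0

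In the re-simulation, Level -1 receives at least one cohort in 22.9, 35.6, 60.3 and 79.4% of trials in Scenarios 1-4.

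**4. Effect on the Level -1 rate: illustration on assumed values only**

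The documents give no Grade 3/4 adverse event rates for this regimen. Let a be the chance of such an event in induction, m the chance in maintenance among those who reach it, and r the share who reach it, all taken as independent. Then:

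- rate over the whole treatment period = a + (1 − a) × r × m
- rate recorded under 12.1.1 = m

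With r = 0.8 and m = 0.2:

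- a = 0.3: 0.3 + 0.7 × 0.16 = 0.412, against 0.20 recorded
- a = 0.5: 0.5 + 0.5 × 0.16 = 0.580, against 0.20
- a = 0.7: 0.7 + 0.3 × 0.16 = 0.748, against 0.20

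Over a from 0.3 to 0.7, m from 0.1 to 0.3 and r from 0.7 to 0.9, the whole-period rate runs from 0.349 to 0.781 and the recorded rate from 0.10 to 0.30. Under this model the recorded rate is the lower one whenever m is no larger than a.

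**The case against.** The strongest reply is that nothing ties the 12.1.1 sentence to the primary endpoint. It stands in the chapter on antitumor effect, next to the response definitions. Sections 9.1 and 9.3 neither cite it nor speak of an evaluable subset. Its opening words sound inclusive, and the likeliest explanation is that Level -1 was overlooked. An analyst who counts from Cycle 1 Day 1 will see no effect at all. This stands as a limit on the consequence. It does not remove the defect: a primary endpoint with no population of its own should not depend on the analyst setting aside the only general rule on toxicity evaluability.

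Three stronger readings are tempting, and the documents do not support them.

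- **That the dose finding is compromised.** A reader might infer that Level -1 patients cannot contribute DLTs. Section 6.2 opens the DLT window at Cycle 1 Day 1 for every level under its own evaluability rule, and the BOIN count follows that rule.
- **That Section 6.2 compounds the problem.** One of its lists applies to "DLTs if felt to be possibly, probably, or definitely related to entinostat", so in an entinostat-free Cycle 1 only the three hematologic items, which count for any study drug, can register. This fits the aim of finding an entinostat MTD, and Section 9.1 explains why hematologic events count despite uncertain attribution. It is not a defect.
- **That the Level -1 induction events are lost, or that Level -1 will be judged safe without them.** Section 10.4 requires routine reporting of all adverse events, and the Section 11 calendar evaluates them from Cycle 1 Day 1. Section 9.1.1 calls for review of all available safety data at the end of the trial, when a recommended phase 2 dose below the MTD may be chosen.

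It is also fair to object that neither 9.1 nor 9.3 plans a pooled rate, and that use of Level -1 depends on which hypothetical scenario holds.

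**Conclusion.** Wrong as written, minor to moderate severity. Under the literal definition, the primary Grade 3/4 rate at Level -1 leaves out induction events and patients who never reach maintenance, while Levels 1-3 count from Cycle 1 Day 1, so the rates are not comparable across levels. The harm is to the reported Level -1 rate, and to a pooled rate if one is produced.

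The point rests on two conditions: the analyst applies 12.1.1 to the endpoint, and the trial de-escalates to Level -1. On the plan's own simulations the second condition involves about 1.3 to 8.0 patients per trial on average, and Level -1 is the selected dose in 2.89 to 51.73% of trials, most often where toxicity is high. The size of the shift in the rate cannot be derived from the documents; the illustrated values are assumptions.

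**What to change.** In Section 12.1.1, start toxicity evaluability at the first dose of any study drug in place of the first dose of entinostat. Leave Section 6.2, the BOIN table and Section 9.1.3 as they are.

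The cost is one phrase in an amendment. It needs no new data, visits or patients, and it leaves DLT counts, dose decisions, stopping, MTD selection and operating characteristics unchanged. At Levels 1-3 it changes essentially nothing, because entinostat is already the first drug given. The Level -1 rate will then include toxicity from carboplatin, etoposide and atezolizumab during induction, as the rates at the other levels already do.

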#### 12.1.2 Disease Parameters

Measurable Disease. Measurable lesions are defined as those that can be accurately measured in at least one dimension (longest diameter to be recorded) as  $\geq 20$  mm ( $\geq 2$  cm) by chest x-ray or as  $\geq 10$  mm ( $\geq 1$  cm) with CT scan, MRI, or calipers by clinical exam. All tumor measurements must be recorded in millimeters (or decimal fractions of centimeters).

Note: Tumor lesions that are situated in a previously irradiated area might or might not be considered measurable.

Malignant Lymph Nodes. To be considered pathologically enlarged and measurable, a lymph

node must be  $\geq 15$  mm ( $\geq 1.5$  cm) in short axis when assessed by CT scan (CT scan slice thickness recommended to be no greater than 5 mm [0.5 cm]). At baseline and in follow-up, only the short axis will be measured and followed.

**Non-Measurable Disease.** All other lesions (or sites of disease), including small lesions (longest diameter  $< 10$  mm [ $< 1$  cm] or pathological lymph nodes with  $\geq 10$  to  $< 15$  mm [ $\geq 1$  to  $< 1.5$  cm] short axis), are considered non-measurable disease. Bone lesions, leptomeningeal disease, ascites, pleural/pericardial effusions, lymphangitis cutis/pulmonitis, inflammatory breast disease, and abdominal masses (not followed by CT or MRI), are considered as non-measurable.

Note: Cystic lesions that meet the criteria for radiographically defined simple cysts should not be considered as malignant lesions (neither measurable nor non-measurable) since they are, by definition, simple cysts.

‘Cystic lesions’ thought to represent cystic metastases can be considered as measurable lesions, if they meet the definition of measurability described above. However, if non-cystic lesions are present in the same patient, these are preferred for selection as target lesions.

**Target Lesions.** All measurable lesions up to a maximum of 2 lesions per organ and 5 lesions in total, representative of all involved organs, should be identified as **target lesions** and recorded and measured at baseline. Target lesions should be selected on the basis of their size (lesions with the longest diameter), be representative of all involved organs, but in addition should be those that lend themselves to reproducible repeated measurements. It may be the case that, on occasion, the largest lesion does not lend itself to reproducible measurement in which circumstance the next largest lesion which can be measured reproducibly should be selected. A sum of the diameters (longest for non-nodal lesions, short axis for nodal lesions) for all target lesions will be calculated and reported as the baseline sum diameters. If lymph nodes are to be included in the sum, then only the short axis is added into the sum. The baseline sum diameters will be used as reference to further characterize any objective tumor regression in the measurable dimension of the disease.

**Non-Target Lesions.** All other lesions (or sites of disease) including any measurable lesions over and above the 5 target lesions should be identified as **non-target lesions** and should also be recorded at baseline. Measurements of these lesions are not required, but the presence, absence, or in rare cases unequivocal progression of each should be noted throughout follow-up.

